#### **5.7.2.2 Treatment Compliance and Modifications**

Action on study drug will be summarized across the cycles

## 5.8 Efficacy Analyses

The investigator's assessment of response including tumor lesion measurement (targeted and non-targeted), new lesions, will be provided in a data listing.

## 5.9 Pharmacokinetic, Pharmacodynamic, and Biomarker Analysis

### 5.9.1 Pharmacokinetic Analyses

The PK population will be used for the description of the concentration-time profiles and for the estimation of the PK parameters.

Descriptive statistics (number of patients, mean, SD, geometric mean, median, minimum, maximum, and coefficient of variation) will be presented for the plasma PK parameters listed below. Individual and mean plasma concentration data will be plotted over time.

Data permitting, summary statistics for the following PK parameters will be provided:

- Area under the plasma concentration-time curve from time 0 to time of last measurable concentration( $AUC_{last}$ )
- Area under the plasma concentration-time curve from time 0 to infinity ( $AUC_{inf}$ )
- Area under the plasma concentration-time curve from time 0 to 48 hr ( $AUC_{48hr}$ )
- Observed maximum plasma concentration ( $C_{max}$ )
- Time to observed maximum plasma concentration ( $T_{max}$ )
- Terminal disposition phase rate constant ( $\lambda_z$ )
- Terminal phase half-life ( $t_{1/2}$ )
- Apparent clearance (CL/F)
- Apparent terminal phase volume of distribution ( $V_z/F$ )

QTc-PK analyses will be performed by Metrum Research Group. The details are presented in a SAP prepared by Metrum Research Group.

### 5.9.2 Pharmacodynamic Analyses

Not applicable.

**MLN0128**  
**Statistical Analysis Plan, Study C31002**

**5.9.3 Biomarker Analysis**

Not applicable.

**5.10 Safety Analyses**

Safety evaluations will be based on the incidence, severity, type of AEs, clinically significant changes or abnormalities in the patient's weight, vital signs, ECG, and clinical laboratory results.

These analyses will be performed using the safety population.

**5.10.1 Adverse Events**

**5.10.1.1 Adverse Events**

AEs will be coded using the Medical Dictionary for Regulatory Activities ( MedDRA), version 17.0 or higher.

A treatment-emergent AE (TEAE) is an AE that occurs on or after the date of the first dose of study drug and up through 30 days after the last dose of study drug.

The number and percentage of patients experiencing at least 1 TEAE will be tabulated by MedDRA primary system organ class, high-level term and preferred term. For the number of patients with AEs, patients reporting the same event more than once will have that event counted only once within each body system, once within each high- level term, and once within each preferred term.

Tabular summaries of the following TEAEs will also be provided:

- TEAEs related to Study Drug
- Grade 3 or greater TEAEs
- Grade 3 or greater TEAEs related to Study Drug
- Most common ( $\geq 10\%$  of patients) TEAEs by maximum severity grade

The following adverse events of interest will be tabulated:

Adverse event of interest	MedDRA Preferred Term
Hyperglycemia	Glucose tolerance impaired, Hyperglycaemia, Impaired fasting glucose
Rash	Fixed eruption, Mucocutaneous rash, Rash, Rash generalized, Rash macular, Rash maculo-papular, Rash maculovesicular, Rash morbilliform, Rash rubelliform, Rash scarlatiniform, Rash vesicular, Dermatitis exfoliative, Drug eruption, Drug hypersensitivity, Drug rash with eosinophilia and systemic symptoms, Reaction to drug excipients, Toxic skin eruption, Administration related reaction, Erythema, Generalised erythema, Rash erythematous, Rash popular, Rash papulosquamous
Renal Insufficiency (MedDRA Standardized Medical Query)	Acute phosphate nephropathy , Acute prerenal failure (Narrow), Anuria (Narrow), Azotaemia (Narrow), Continuous haemodiafiltration (Narrow), Dialysis (Narrow), Haemodialysis (Narrow), Neonatal anuria (Narrow), Nephropathy toxic (Narrow), Oliguria (Narrow), Peritoneal dialysis (Narrow), Prerenal failure (Narrow), Renal failure (Narrow), Renal failure acute (Narrow), Renal failure neonatal (Narrow), Renal impairment (Narrow), Renal impairment neonatal (Narrow), Albuminuria (Broad), Blood creatinine abnormal (Broad), Blood creatinine increased (Broad), Blood urea abnormal (Broad), Blood urea increased (Broad), Blood urea nitrogen/creatinine ratio, Creatinine renal clearance abnormal, Creatinine renal clearance decreased, Creatinine urine abnormal (Broad), Creatinine urine decreased (Broad), Crystal nephropathy (Broad), Glomerular filtration rate abnormal, Glomerular filtration rate decreased, Hypercreatininaemia (Broad), Nephritic syndrome (Broad), Nephritis (Broad), Oedema due to renal disease (Broad), Protein urine present (Broad), Proteinuria (Broad), Renal function test abnormal (Broad), Renal transplant (Broad), Renal tubular disorder (Broad), Renal tubular necrosis (Broad), Tubulointerstitial nephritis (Broad), Urea renal clearance decreased (Broad), Urine output decreased (Broad)

Mucosal Inflammation	Burning sensation mucosal, Mucosal erosion, Mucosal excoriation, Mucosal exfoliation, Mucosal hyperaemia, Mucosal inflammation, Mucosal necrosis, Mucosal ulceration, Aphthous stomatitis, Mouth ulceration, Oral mucosa erosion, Stomatitis, Stomatitis haemorrhagic, Stomatitis necrotizing, Oral discomfort, Oral mucosal blistering, Oral mucosal erythema, Oral mucosal exfoliation, Oropharyngeal blistering, Oropharyngeal discomfort, Oropharyngeal pain
Asthenic Conditions	Asthenia, Fatigue, Lethargy, Listless, Malaise, Sluggishness, Muscle Weakness

Events will be considered related to study drug if the investigator answered “yes” to the following question: “Is there a reasonable possibility that the adverse event was associated with the study medication?”

Intensity is determined using the National Cancer Institute Common Toxicity Criteria (NCI CTC) version 4.03.

By-patient listings will be produced for all DLTs.

All TEAEs will be presented in by-patient listings.

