- a Screening assessments are performed within 28 days before the C1D1 MLN0128 dose. Screening assessments performed no more than 3 days before Screening; Day -1 will qualify as baseline assessments and need not be repeated, unless otherwise specified. Screening; Day -1 is defined as the day before first dose of study drug; screening assessments must be completed by Screening; Day -1.
- b Patients will attend an EOS/Early Termination visit 30 to 40 days after receiving their last dose of MLN0128.
- c Vital sign measurements include blood pressure (diastolic and systolic), heart rate, and temperature.
- d The C1D1 single, 12-lead ECG can be collected 2-4 hours after dosing.
- e When the timing of a PK or safety laboratory blood sample coincides with the timing of ECG measurements, the ECG will be completed before the collection of the blood sample.
- f Baseline CT (with contrast) or MRI scan of the chest, abdomen, and pelvis must be obtained within 4 weeks before the first dose of MLN0128 and at C3D28, after which point CT (with contrast) or MRI may be performed Q3C (ie, C6D28, C9D28, C12D28, etc) as clinically indicated, according to standard of care. The same imaging modality (CT [with contrast] or MRI) should be used throughout the study. Scans are permitted up to 7 days in advance of the study visit. For long term patients, defined as study participation (≥ 1 year, a CT (with contrast)/MRI of chest, abdomen, and pelvis will be obtained at intervals of up to every 4 cycles (plus or minus 7 days) as clinically indicated.
- g Including serious pretreatment events; see Section 9.1.1 for definition.
- h A single dose of 40 mg MLN0128 will be administered on C1D1; patients continuing treatment with MLN0128 after C1D3 at the discretion of the investigator will receive a maximum dose of 30 mg MLN0128 administered on a QW schedule.
- i Patients will be administered an antiemetic agent (0.25 mg palonosetron) as an intravenous infusion over 30 seconds, at least 30 minutes before study drug administration.

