For the Screening; Day -1 and Cycle 1, Day 1 study visits, fasting serum glucose will be measured at the clinical facility. In addition, all patients will be issued a glucometer and trained to use it to monitor their daily predose fasting blood glucose (FBG) levels at home for the days on which glucose is not measured at the clinic. Patients will be instructed to notify the study staff immediately with any abnormal readings (ie, ≥ 150 mg/dL) for further instructions on the management of hyperglycemia. In-home glucose monitoring is not required on days when fasting glucose is measured in the clinic.

To mitigate nausea and vomiting known to occur at a 40 mg dose of MLN0128, patients will be administered an antiemetic agent (0.25 mg palonosetron) on Cycle 1, Day 1.

After collection of the 10-hour postdose PK/ECG assessment on Cycle 1, Day 1, patients will be furloughed from the study site. The Holter recorders will not be removed during this furlough period.

MLN0128**Clinical Study Protocol C31002 Protocol Amendment 2**

On Cycle 1, Day 2 and Cycle 1, Day 3, patients may eat and drink up to approximately 2 hours before arriving at the study site for PK/ECG evaluations.

On Cycle 1, Day 2, patients will report to the clinical facility at least 1 hour before the 24-hour postdose PK/ECG (triplicate) assessments. After the PK/ECG assessments are completed, the Holter recorders will be removed and patients will be furloughed from the study site.

On Cycle 1, Day 3, patients will report to the clinical facility at least 1 hour before the 48-hour postdose assessments, which will represent the final study endpoint-specific planned PK/ECG assessments.

Patients may continue to receive MLN0128 if, in the opinion of the investigator, the patients are deriving clinical benefit, until they experience disease progression. Patients continuing treatment with MLN0128 at the discretion of the investigator will receive a dose of MLN0128 up to 30 mg QW. Dose escalation will not be permitted, and a maximum of 2 dose reductions (for patients experiencing study drug-related toxicity) will be permitted. Patients will return to the study site for follow-up visits at the time points in the [Schedule of Events](#). Treatment may continue until disease progression, unacceptable MLN0128-related toxicity, withdrawal of consent, or for up to 12 months (whichever occurs first).

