After completing the required PK/ECG assessment period (Cycle 1, Day 3), patients may continue treatment with MLN0128 at the discretion of the investigator at a dose of MLN0128 30 mg QW. If patients experience severe emesis or mucositis preventing them from taking an MLN0128 dose, that dose will be skipped. If emesis occurs after study medication ingestion and whole capsule(s) are visible in the vomitus, replacement capsule(s) should be taken; otherwise the dose will not be re-administered, and patients should adhere to the dosing schedule and resume dosing at the next scheduled time with the prescribed dosage. Patients should record the time of the emesis in their dosing diary cards (see the Study Manual). Under no circumstance should a patient repeat a dose or double-up doses. Patients should be instructed to take their study medication at approximately the same time each week and not to take more than the prescribed dose at any time. Patients should swallow the study medication whole and not chew it, open it, or manipulate it in any way before swallowing. In the event, that, a patient fails to take the MLN0128 dose within the time frame specified (\pm 12 hours), that dose should be skipped. Patients should record any skipped doses in their dosing diary cards (see the Study Manual) and resume dosing at the next scheduled time with the prescribed dosage.

Starting at Cycle 1, Day 8, patients are advised to take their doses of study drug with a light meal.

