### **5.7.2 Study Treatments**

Patients will be required to swallow 8, 5-mg capsules for a total dose of 40 mg MLN0128 on Cycle 1, Day 1. To mitigate nausea and vomiting, patients will be administered an antiemetic agent on Cycle 1, Day 1 as an intravenous infusion (IV) over 30 seconds, at least 30 minutes before study drug administration. After completing the required PK/ECG assessments at Cycle 1, Day 3, patients may continue treatment with MLN0128. For patients continuing treatment with MLN0128, the drug is administered at a dose of 30 mg once weekly (QW) in continuous cycles of 28 days.

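### The TEAE and SAE tables use one window for the single 40 mg dose and all later weekly dosing, so no planned summary shows tolerability after 40 mg or gives continuation-dose rates their own denominator

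*SAP*

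**What the plan says.** **Dosing.** Footnote h of the protocol's Schedule of Events says: "A single dose of 40 mg MLN0128 will be administered on C1D1". Protocol 4.1 then makes further treatment conditional: "Patients may continue to receive MLN0128 if, in the opinion of the investigator, the patients are deriving clinical benefit". It sets the later dose as follows: "Patients continuing treatment with MLN0128 at the discretion of the investigator will receive a dose of MLN0128 up to 30 mg QW". SAP 5.7.2 says of continuing patients that "the drug is administered at a dose of 30 mg once weekly (QW) in continuous cycles of 28 days". Protocol 4.1 limits treatment to 12 months, and protocol 4.3 allows longer after discussion with the sponsor.

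**Conditions around each dose.** On Cycle 1, Day 1, patients receive palonosetron and do not eat from 2 hours before to 4 hours after dosing (protocol 6.1). After that, protocol 6.1 says: "Starting at Cycle 1, Day 8, patients are advised to take their doses of study drug with a light meal".

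**Safety tables.** SAP 5.10.1.1 defines a TEAE as "an AE that occurs on or after the date of the first dose of study drug and up through 30 days after the last dose". Protocol 8.1.9 uses the same window. The tables of all, drug-related, Grade 3 or greater and most common TEAEs, of events of interest, and of SAEs (SAP 5.10.1.2) are all in the safety population, which is every patient with at least one dose (SAP 2.1). A patient counts once per term, and the most common TEAEs are shown at maximum grade. No table is split by dose, period, cycle or continuation status.

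**The concern.** The trial is built around one 40 mg dose. It is the dose named in the primary objective, and the protocol expects nausea and vomiting at it. A reader of the study report will want to know how that dose was tolerated. A single pooled percentage combines three things that differ:

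- **Dose and conditions.** One 40 mg dose with a mandated antiemetic and restricted food is combined with repeated doses of 30 mg or less, taken with a light meal and with antiemetics as needed.
- **Who is exposed.** All patients receive 40 mg. Only those judged to be benefiting receive the continuation dose, yet continuation events are divided by all dosed patients.
- **Follow-up.** A patient who stops after the first dose is observed for about 30 days. A long-term continuer can be observed for more than a year.

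Because counting is once per patient over the whole window, and the most common events are shown at their worst grade, neither count nor grade in these tables can be traced to a dose. At stake is whether the trial describes 40 mg tolerability in a prespecified summary, and whether the continuation dose gets a rate on its own denominator.

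**Working it through.** The documents give no figure on this point to reproduce. What can be checked is whether any planned summary separates the periods, and what the schedule implies for the windows.

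**1. Search for a split.** SAP 5.10.1.1 and 5.10.1.2 contain none, and SAP section 6 adds no analysis. SAP 5.7.2.1 summarises exposure by cycle, but that is not an adverse event table, and Cycle 1 holds both the 40 mg dose and later doses. Laboratory summaries by visit do not help either: after Day 1, hematology and chemistry are next scheduled on Day 15 (Schedule of Events), after the first continuation dose that protocol 6.1 implies on Day 8.

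**2. Doses and windows.** Inputs: 28-day cycles with weekly dosing (protocol 6.1), so 4 doses per cycle on Days 1, 8, 15 and 22, and follow-up of 30 days after the last dose (SAP 5.10.1.1). For a patient completing *k* cycles:

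- doses of 40 mg: 1
- later doses of at most 30 mg: 4*k* − 1
- day of last dose: 28*k* − 6
- last day of the TEAE window: 28*k* − 6 + 30 = 28*k* + 24
- share of the window in Days 1-7: 7 / (28*k* + 24)

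| Patient | 40 mg doses | Later doses | Window ends on day | Days 1-7 as share |
|---|---|---|---|---|
| Single dose only | 1 | 0 | 1 + 30 = 31 | 22.6% |
| 1 cycle | 1 | 3 | 52 | 13.5% |
| 3 cycles | 1 | 11 | 108 | 6.5% |
| 6 cycles | 1 | 23 | 192 | 3.6% |
| 13 cycles (about 12 months) | 1 | 51 | 388 | 1.8% |

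The longest of these windows is 388 / 31 = 12.5 times the shortest, before any extension beyond 12 months.

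**3. Direction of the effect.** Let N be all dosed patients, A those with the event after 40 mg and before any continuation dose, and B those with it after a continuation dose. The planned table shows |A ∪ B| / N.

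- Against the 40 mg period: |A ∪ B| / N ≥ |A| / N. The pooled figure is never lower than the 40 mg-period incidence.
- Against the continuation dose: the relevant rate is |B| / N_c, with N_c the continuing patients. For an event seen only in continuation, the planned table shows |B| / N, which is lower by the factor N / N_c. If 50% to 100% of patients continue (an assumption; the documents give no rate), that factor runs from 2 to 1. For events seen in both periods, the pooled figure may lie on either side.

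**4. Size.** Turning this into percentages needs event rates by period, the proportion continuing and time on treatment. None is in the documents. Any figure built on assumed weekly rates would mainly reflect the longer follow-up and would rise even if the dose never changed. No such figure is given here.

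**The case against.** The strongest reply is that the plan answers the objective it states. The secondary objective concerns the safety and tolerability of MLN0128 in general; only the primary QTc objective names the 40 mg dose. The SAP window agrees with protocol 8.1.9, and no table is labelled a 40 mg profile. A reader might infer that the SAP departs from the protocol or fails its safety objective. The documents do not support that: the pooled tables are a valid any-exposure summary.

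Nor is the information lost. About 30 patients are planned, the analysis is descriptive, and TEAEs, DLTs, SAEs, deaths and discontinuation events are all listed by patient. Protocol 8.1.9 also permits additional safety analyses. It would therefore be too strong to say that 40 mg tolerability cannot be recovered. If the listings show onset dates, it probably can be, by hand. What stands is that no such summary is prespecified, and that a permission to do more is not a plan.

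A reader might also assume that every patient offers a clean, equal-length period after 40 mg. That fails too. Under protocol 6.1 the next dose is skipped for severe emesis or mucositis, or if missed by more than 12 hours, so the period before the first continuation dose can be longest in patients with toxicity. Laboratory events first found at the Day 15 visit cannot be cleanly assigned to 40 mg. These limits affect how the periods should be defined, but they do not remove the gap.

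**Conclusion.** The point holds as a cheap improvement. The planned tables pool one 40 mg dose in all patients with later, lower, repeated dosing in an investigator-selected subset followed for much longer. No planned summary describes tolerability after 40 mg or gives the continuation dose its own denominator.

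The schedule gives the scale of the imbalance: for a continuer completing 1 to 13 cycles, Days 1-7 are 13.5% down to 1.8% of the TEAE window. This assumes that continuation starts on Day 8, as the meal instruction implies, with no skipped doses. The pooled incidence cannot be below the 40 mg-period incidence, but how far above it lies cannot be computed from the documents. The conclusion does not depend on whether the continuation dose is read as up to 30 mg (protocol 4.1) or as 30 mg (protocol 6.1, SAP 5.7.2); those passages should be reconciled.

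**What to change.** Keep the overall tables. In SAP 5.10.1.1 and 5.10.1.2, add TEAE, drug-related TEAE, Grade 3 or greater TEAE and SAE tables by period of onset:

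- **(a) After 40 mg.** Denominator: all dosed patients. From the Cycle 1, Day 1 dose to before the first continuation dose, or to 30 days after the Cycle 1, Day 1 dose if there is none. Add a Days 1-7 version, censored at any earlier continuation dose, to give a common window.
- **(b) Continuation.** Denominator: patients who took at least one continuation dose. From that dose to 30 days after the last dose.

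Together (a) and (b) cover each patient's TEAE window with no gap. In particular, events after Day 7 in patients who do not continue, which follow 40 mg alone, stay in (a).

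Extend SAP 5.4.1.1, which at present resolves partial dates only to treatment-emergent or not, with a rule for assigning the period. One option is to assign the event to the 40 mg period unless the known parts of the date rule that out.

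**Cost.** SAP wording and a few extra tables from onset and dosing dates already collected; no change to conduct or sample size. The remaining weakness is that late-onset effects of the 40 mg dose, or laboratory events first detected at the Day 15 visit, can fall in the continuation period. A footnote should say so, and it is a further reason to keep the overall tables.

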9.1.2 Adverse Event Definition

AE means any untoward medical occurrence in a patient or subject administered a pharmaceutical product; the untoward medical occurrence does not necessarily have a causal relationship with this treatment. An AE can therefore be any unfavorable and unintended sign (including an abnormal laboratory finding), symptom, or disease temporally associated with the use of a medicinal (investigational) product whether or not it is related to the medicinal product. This includes any newly occurring event, or a previous condition that has increased in severity or frequency since the administration of study drug.

An abnormal laboratory value will not be assessed as an AE unless that value leads to discontinuation or delay in treatment, dose modification, therapeutic intervention, or is considered by the investigator to be a clinically significant change from baseline.

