9.2 Procedures for Recording and Reporting Adverse Events and Serious Adverse Events

All AEs spontaneously reported by the patient and/or in response to an open question from study personnel or revealed by observation, physical examination, or other diagnostic procedures will be recorded on the appropriate page of the eCRF (see Section 9.3 for the period of observation). Any clinically relevant deterioration in laboratory assessments or other clinical finding is considered an AE. When possible, signs and symptoms indicating a common underlying pathology should be noted as 1 comprehensive event.

Regardless of causality, SAEs and serious pretreatment events (as defined in Section 9.1) must be reported (see Section 9.3 for the period of observation) by the investigator to the Millennium Department of Pharmacovigilance or designee (contact information provided below). This should be done by faxing the SAE Form within 24 hours after becoming aware of the event. The SAE Form, created specifically by Millennium, will be provided to each clinical study site. A sample of the SAE Form may be found in the Study Manual. Follow-up information on the SAE or serious pretreatment event may be requested by Millennium. SAE report information must be consistent with the data provided on the eCRF.

SAE Reporting Contact Information

Cognizant

US and Canada

[contact]

Email: [contact]

Planned hospital admissions or surgical procedures for an illness or disease that existed before study drug was given are not to be considered AEs unless the condition deteriorated in an unexpected manner during the trial (eg, surgery was performed earlier or later than planned).

For both serious and nonserious AEs, the investigator must determine both the intensity of the event and the relationship of the event to study drug administration. For serious

pretreatment events, the investigator must determine both the intensity of the event and the relationship of the event to study procedures.

Intensity for each AE, including any lab abnormality, will be determined using the NCI CTCAE, Version 4.03, effective date 14 June 2010.⁽¹³⁾ The criteria are provided in the Study Manual.

Relationship to study drug administration will be determined by the investigator responding yes or no to this question: Is there a reasonable possibility that the AE is associated with the study drug?

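### The hyperglycemia event-of-interest group in SAP 5.10.1.1 has no blood-glucose measurement term, so a patient whose glucose event is coded only that way would not be counted in it

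*SAP*

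**What the plan says.** SAP 5.10.1.1 introduces a table with the words "The following adverse events of interest will be tabulated" and defines each of five groups by the preferred terms listed beside it. The hyperglycemia row reads "Glucose tolerance impaired, Hyperglycaemia, Impaired fasting glucose" and ends there. The renal row is labelled as a standardized MedDRA query, with most terms marked narrow or broad, and it contains measurement terms: "Blood creatinine abnormal (Broad), Blood creatinine increased (Broad), Blood urea abnormal (Broad), Blood urea increased (Broad", and others such as decreased glomerular filtration rate.

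Protocol 9.1.2 says that an abnormal laboratory value is not an adverse event "unless that value leads to discontinuation or delay in treatment, dose modification, therapeutic intervention", or the investigator considers it a clinically significant change from baseline. Protocol 9.2 adds: "Any clinically relevant deterioration in laboratory assessments or other clinical finding is considered an AE".

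Protocol 6.8.2 makes glucose-lowering treatment mandatory from Grade 2 upward. At Grade 1, Table 6-3 lists an oral agent, while the text below it lets the investigator choose between monitoring and treatment. Those two statements need to be reconciled, but the present point does not depend on how.

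**The concern.** Hyperglycemia is an expected effect of this drug. It has its own management section, home glucose monitoring and its own exception in the dose-limiting toxicity definition. The event-of-interest row is the one planned count of how many patients had it.

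Because the row is a closed list, a term that is not listed is not counted. A glucose rise that is treated is an adverse event under 9.1.2, and many rises will first be seen as a number on a glucometer or laboratory report. If a site reports the number and the coder assigns a measurement term, the patient does not enter the row. The count then depends partly on how sites word the event, and any error can only lower it. The renal row does not have this gap for creatinine and urea, so the two rows cannot be read on the same footing.

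**Working it through.** The documents state no expected or observed hyperglycemia rate, so there is no plan figure to reproduce. The check sets the passages side by side and then shows how large the effect could be.

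**Can such an event arise and miss the row?**

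1. A glucose value that leads to treatment is an adverse event (Protocol 9.1.2). Treatment is mandatory from Grade 2 (Protocol 6.8.2), so treated rises are to be expected.
2. Neither Protocol 9.2 nor 6.8.2 tells sites to report such an event under the word hyperglycemia. Laboratory-style wording is therefore possible.
3. Measurement-worded adverse events do occur in this program: Protocol 1.5 includes increased blood creatinine among the common events seen with the drug. It gives no such example for glucose.
4. None of the three terms in the hyperglycemia row is a blood-glucose measurement term. An event coded to one would not match the row.

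**Where would it still appear?** In the overall TEAE table by preferred term, in the related-event and Grade 3 or higher tables if it qualifies, and in the by-patient TEAE listing (SAP 5.10.1.1). Glucose values are also summarized, plotted and graded in shift tables (SAP 5.10.2). These do not give the grouped patient count directly. Preferred-term counts cannot be added, because one patient may appear under several terms, and shift tables grade values without showing whether an event was reported or judged related. A hand count from the listing would be needed.

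**Size.** Let p be the true share of patients with a glucose adverse event, m the share of those patients whose events are coded only under unlisted measurement terms, and N the number of patients.

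- Tabulated rate = p × (1 − m)
- Expected patients missed = N × p × m
- Loss per missed patient = 100 / N percentage points

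N is about 30 (Protocol 4.2), so each missed patient costs 100 / 30 = 3.3 percentage points. Both p and m are assumptions; the documents give neither.

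| Assumed p | m = 0 | m = 10% | m = 20% | m = 30% |
|---|---|---|---|---|
| 30% | 30% (0 missed) | 27% (0.9) | 24% (1.8) | 21% (2.7) |
| 50% | 50% (0) | 45% (1.5) | 40% (3.0) | 35% (4.5) |
| 70% | 70% (0) | 63% (2.1) | 56% (4.2) | 49% (6.3) |

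Example: p = 50% and m = 20% give 50% × 0.80 = 40%, and 30 × 0.50 × 0.20 = 3 patients missed. The loss is relative: m = 20% removes a fifth of the true rate, which here is 10 percentage points.

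**The case against.** The strongest reply is that the protocol itself calls this event hyperglycemia throughout: in the dose-limiting toxicity definition, in the heading and grades of Table 6-3, and in the text on home readings. Section 9.1.2 says when a value becomes an adverse event, not how it is to be worded. A site that follows the protocol's vocabulary will report a term that is in the row. This stands. It means that m may be small or zero, and no document shows a glucose event reported in measurement wording.

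A reader might therefore go too far by inferring that treated glucose rises are left out of the row as a matter of course. The documents do not support that; only a patient coded solely under a measurement term is missed. Nor do they support saying that the row holds only diagnoses, since impaired fasting glucose is close to a test result. The gap is narrower: no blood-glucose measurement term is listed.

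It can also be said that the renal row is openly labelled as a standardized query with broad terms, that the other rows carry no such label, and that copying its scope is a matter of preference. It is true that the difference is not hidden and that the renal row is the exception among five. But the label explains the difference without giving a reason to leave measurement terms out for a toxicity that is itself detected by measurement.

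Finally, the events are reported elsewhere, in a descriptive study with no hypothesis tests. That also stands, and it limits the point to one grouped count.

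**Conclusion.** The point holds as a small, conditional gap in a secondary safety summary. The hyperglycemia row would undercount any patient whose glucose event is coded only under an unlisted measurement term. The tabulated rate is then the true rate times (1 − m), at about 3.3 percentage points per missed patient. The value of m is unknown and may be zero, so the documents cannot show that an undercount will occur. They show only that nothing in the row prevents one and that it could run in one direction only. Reported events stay in the overall TEAE table and the listings, and the primary QTc endpoint is untouched. The change is worth making because it is cheap, not because the present list is shown to mislead.

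**What to change.** Before database lock, add to the hyperglycemia row of the SAP 5.10.1.1 table the coding dictionary's preferred terms for increased or abnormal blood glucose. The documents do not name these terms, so take the exact wording from the MedDRA version in use (SAP: version 17.0 or higher).

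The cost is one row of a table and the matching line in the program. No new data and no change to any clinical rule are needed. The one downside is that the reported rate may rise somewhat and include milder laboratory-only events; a footnote naming the added terms would let readers see this. If no event is coded to them, the table does not change.
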